#### Potential for improved treatment regimens and compliance

For people already using basal insulin to manage diabetes, availability of basal insulin administered weekly may improve treatment compliance and lead to better real-world patient outcomes. A weekly insulin with a lower peak-to-trough profile across a week and a nearly flat within-day insulin profile could also reduce within-day glucose variability and result in more consistent and predictable glycemic control.

#### LY3209590

LY3209590 is a novel insulin receptor agonist that is in development as a once-weekly basal insulin for the treatment of hyperglycemia in patients with T2D and T1D. LY3209590 has the potential to decrease patient burden, overcome barriers to initiation of insulin therapy, and may improve glycemic control and quality of life for these patients.

A detailed description of the chemistry, pharmacology, non-clinical and clinical efficacy, and safety of LY3209590 is provided in the IB.

#### *Summary of clinical results*

Phase 1 and Phase 2 studies, including healthy participants and participants with T1D or T2D, have been completed to assess the PK/PD, safety, and efficacy of LY3209590. The results thus far support continued development of LY3209590 as a treatment for diabetes mellitus.

*Phase 1 results*

LY3209590 pharmacokinetics show a low peak-to-trough ratio and extended half-life that supports once-weekly dosing.

Single-ascending doses of LY3209590 lowered fasting glucose in a dose- and concentration-dependent manner, with a prolonged time-action profile.

Overall, LY3209590 was well tolerated in healthy participants and participants with T2D.

*Phase 2 Study BDCM results*

Phase 2 Study BDCM evaluated the effects of LY3209590 on glycemic control using 2 different dosing algorithms compared with insulin degludec in study participants with T2D previously treated with basal insulin. The two LY3209590 dosing algorithms and the degludec dosing algorithm each had a different FBG target.

Safety data indicate that there was no increased risk with LY3209590 treatment compared to insulin degludec.

LY3209590, when administered according to either dosing algorithm, was noninferior to insulin degludec for glycemic control as measured by change in HbA1c after 32 weeks of treatment.

Treatment differences in FBG were consistent with the preset FBG targets of the dosing algorithms used.

## **2.3. Benefit/Risk Assessment**

More detailed information about the known and expected benefits and risks and reasonably expected AEs of LY3209590 may be found in the IB.

More detailed information about the known and expected benefits and risks and reasonably expected AEs of insulin glargine may be found in the local product package insert.

### **2.3.1. Risk Assessment**

#### **Potential risks for this study**

The potential risks associated with LY3209590 include

- hypoglycemia
- hyperglycemia
- hypersensitivity reaction
- injection-site reactions, for example, injection-site rash, erythema, pruritus, or lipohypertrophy
- immunogenicity, and
- cardiovascular risks.

It is expected that the known risks would be similar to other insulins.

Safety data available to date suggests that there is no increased risk to participants' safety with LY3209590 treatment compared to degludec, a best-in-class basal insulin.

## **Management of risks**

Sections 5.1, 5.2, 6.8.1, 7, and 8.3 address known potential risks associated with LY3209590.

### ***Protocol risk management measures***

#### *Participant education for hypoglycemia*

After signing informed consent, all participants will be educated about signs and symptoms of hypoglycemia, how to treat hypoglycemia, and how to collect appropriate information for each episode of hypoglycemia. Hypoglycemia may be identified by spontaneous reporting of symptoms from participants, whether confirmed or unconfirmed by simultaneous glucose values, or by blood glucose samples collected between study visits.

#### *Monitoring of participant blood glucose levels*

Each participant will have a study-provided glucometer that will wirelessly transfer participant SMBG to their study-provided e-diary. Participants should use the glucometer to check glucose values whenever hypoglycemia is experienced or suspected.

A web-interface and reporting system will be available for use by study personnel to view participant e-diary entries, including SMBG, insulin doses, and hypoglycemia information throughout the study. Automated alerts will be transmitted to the investigator any time the participant reports a potential severe episode of hypoglycemia, defined as requiring assistance due to neurological impairment, in the e-diary.

#### *Dose modification*

The visit schedule allows for close clinical oversight and dose modification.

The dosing algorithm used in the study requires consideration and adjustment of insulin dosing by the investigator based on participant FBG and hypoglycemia events (see Section 6.5).

All participants will be treated with basal-bolus MDI therapy, which will be titrated to glycemic targets and as clinically indicated for hyperglycemia.

### **2.3.2. Benefit Assessment**

Participants may benefit by receiving personal health information, routine safety assessments, and frequent engagement with health care providers during the study which provide opportunities for coaching and support.

The weekly administration of LY3209590 along with prandial insulin has the potential to offer more consistent glycemic control.

### **2.3.3. Overall Benefit Risk Conclusion**

Considering the clinical data to date and measures taken to minimize risk for the participants in this study, the potential risks identified in association with LY3209590 are justified by the anticipated benefits that may be afforded to participants with T2D.

### 3. Objectives, Endpoints, and Estimands

Objectives	Endpoints
Primary	
Demonstrate noninferiority of LY3209590 compared to insulin glargine on glycemic control.	Change in HbA1c from baseline at Week 26
Key Secondary (Multiplicity Adjusted)	
Demonstrate LY3209590 is superior to insulin glargine in the selected parameters of glycemic control.	
 
• Change in HbA1c from baseline at Week 26
 
• The percentage of participants achieving HbA1c <7% at Week 26 without nocturnal hypoglycemia (<54 mg/dL [3.0 mmol/L] or severe) during treatment phase up to Week 26
 
• The event rate of participant-reported clinically significant nocturnal hypoglycemia (<54 mg/dL [3.0 mmol/L] or severe) during treatment phase up to Week 26
 

Other Secondary	
To investigate the effect of LY3209590 compared with insulin glargine in additional parameters of diabetes management.	
 
• Change in fasting glucose measured by SMBG from baseline to Week 26
 
• Time in glucose range between 70 and 180 mg/dL (3.9 and 10.0 mmol/L), inclusive measured during the CGM session that occurs between Week 22 and Week 26
 
• Time in hypoglycemia range with glucose <54 mg/dL (3.0 mmol/L), measured by CGM that occurs between Week 22 and Week 26
 
• Time in hyperglycemia range with glucose >180 mg/dL (10.0 mmol/L), measured by CGM that occurs between Week 22 and Week 26
 
• Glucose variability measured during the CGM session that occurs between Week 22 and Week 26
 
• Insulin dose at Week 26 
 
○ basal
 
○ bolus
 
○ total, and
 
○ basal/total insulin dose ratio.
 
 
 

To investigate the safety of LY3209590 compared with insulin glargine.	
 
• Incidence and rate of composite of Level 2 and 3 hypoglycemia events during treatment period
 
• Body weight change from baseline to Week 26
 

To investigate the treatment impact of LY3209590 compared with insulin glargine on patient-reported outcome measures.	
 
• Treatment experience at Week 26 for DID-EQ
 

Tertiary	

 
• Investigate the treatment impact of LY3209590 compared with insulin glargine on other measures of efficacy, safety, and patient-reported outcomes.
 
	
Efficacy
 
 
• Percentage of participants achieving HbA1c <7% at Week 26
 
• Percentage of participants achieving HbA1c ≤6.5% at Week 26
 
• Change from baseline to Week 26 in fasting serum glucose as measured by central laboratory
 
 
Safety
 
 
• Rate and incidence of Level 2 hypoglycemia events during treatment period
 
• Rate and incidence of Level 3 hypoglycemia events during treatment period
 
• Incidence of positive treatment-emergent antibody of LY3209590
 
 
Patient-reported outcomes
 
 
• Frequency of responses to “Basal Insulin Experience: Likelihood of incorporating into routine” at Week 26
 
• Frequency of responses to “Basal Insulin Experience: Preference” at Week 26
 
• Change in EQ-5D-5L from baseline at Week 26
 

 
• To characterize the PK/PD of LY3209590.
 
	
 
• LY3209590 PK and concentration response relationships to key safety and efficacy measures.
 

Abbreviations: CGM = continuous glucose monitoring; DID-EQ = Diabetes Injection Device Experience Questionnaire; EQ-5D-5L = EuroQol 5 dimensions 5 levels; HbA1c = hemoglobin A1c; SMBG = self-monitoring of blood glucose.

### Primary estimand (for primary objective)

### ***United States registration***

The *primary* clinical question of interest is:

What is the treatment difference between LY3209590 and insulin glargine in change from baseline at Week 26 in HbA1c in study eligible participants regardless of treatment discontinuation for any reason or initiation of rescue therapy?

The ***treatment regimen estimand*** will be used for the primary objective and is described by the attributes in this table.

Treatment Regimen Estimand Attribute	Description
Treatment condition	randomized treatment regardless of treatment discontinuation or initiation of rescue therapy.
Population	targeted study population. See Section 9.2 for details.
Endpoint	change from baseline to Week 26 in HbA1c.
Remaining intercurrent events	none. The 2 intercurrent events, treatment discontinuation for any reason and initiation of rescue therapy, are addressed by the treatment condition of interest attribute.
Population-level summary	difference in mean changes between treatment conditions.

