#### **Treatment period**

##### ***Visit 3 (Week 0): Randomization***

This is the general flow for Visit 3:

- Study personnel confirm enrollment criteria

- Participants are randomly assigned to an intervention group
- Study personnel complete baseline procedures and sample collection
- Study personnel will provide dosing training
- Study personnel or the participant will administer the first study dose of LY3209590. Insulin glargine can be taken at the site or after the visit depending upon whether the study visit timing coincides with the participant's usual time to administer basal insulin. Administered insulin doses will be entered into the e-diary
- Study personnel train participants on administering insulin lispro at mealtimes
- Study personnel will download the CGM
- Participant will continue CGM wear per the SoA, and
- Study personnel complete all visit procedures.

All participants will be treated with insulin lispro as prandial insulin throughout the treatment period as described in Section 6.5.3. Participants assigned to insulin glargine will administer glargine daily after Visit 3.

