## 9.2. Analyses Sets

This table defines the populations for the purpose of analysis.

Analysis Populations or Datasets	Description
Entered Population	All participants who sign the informed consent form.
Randomized Population	All randomized participants. Participants will be analyzed according to the treatment they were assigned.
Modified Intent-to-Treat (mITT) Population	All randomized participants who took at least 1 dose of LY3209590 or insulin glargine. Participants will be analyzed according to the treatment they were assigned.
Efficacy Analysis Set 1 (EAS1) for treatment regimen estimand	The data will include 
 
• mITT Population excluding participants discontinuing the study treatment due to inadvertent enrollment
 
• all measurement regardless of the use of study treatment or rescue medications.
 

Efficacy Analysis Set 2 (EAS2) for efficacy estimand	The data will include 
 
• mITT Population excluding participants discontinuing the study treatment due to inadvertent enrollment
 
• measurement up to the discontinuation of study treatment or the initiation of rescue medications.
 

Safety Analysis Set (SS)	The data will include 
 
• mITT Population
 
• all measurement regardless of the use of study treatment or rescue medications.
 

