**Figure BDCV 2.1. Illustration of graphical multiple testing procedure with initial  $\alpha$  allocation and weights.**

### 3. Analysis Sets

This table defines the populations and data sets for the purpose of analysis.

Analysis Populations/ Data Sets	Description
Entered Population	All participants who sign the informed consent form
Randomized Population	All randomized participants. Participants will be analyzed according to the treatment they were assigned.
Modified Intent-to-Treat (mITT) Population	All randomized participants who took at least 1 dose of study treatment. Participants will be analyzed according to the treatment they were assigned.
Efficacy Analysis Set 1 (EAS1) for treatment regimen estimand on efficacy measures	
The data will include
 
 
• mITT Population, excluding participants discontinuing the study treatment due to inadvertent enrollment, and
 
• all measurements regardless of the use of study treatment or the initiation of rescue therapy.
 

Efficacy Analysis Set 2 (EAS2) for efficacy estimand and for other secondary/tertiary objectives on efficacy measures	
The data will include
 
 
• mITT Population, excluding participants discontinuing the study treatment due to inadvertent enrollment, and
 
• measurements up to the early discontinuation of study treatment or the initiation of rescue therapy.
 
 
The data cutoff for participants who had intercurrent events is defined by the earliest date from below dates for individual participants other than the analysis for study dose:
 
 
• the date of last study dose + 10 days for LY3209590, or +1 day for glargine
 
• the start date of the first treatment of rescue therapy
 
 
The data cutoff for the analysis on study dose is defined by the earliest date from below dates for individual participants:
 
 
• the date of last study dose
 
• the start date of the first treatment of rescue therapy
 

Safety Analysis Set (SS)	
The data will include
 
 
• mITT Population, and
 
• all measurements regardless of the use of study treatment or the initiation of rescue therapy.
 

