#### **4.3.3.2. Including Inadvertently Enrolled Participants**

The primary efficacy analysis will be repeated for the mITT population, including participants inadvertently enrolled, for both treatment regimen estimand and efficacy estimand.

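### The treatment regimen analysis set drops randomized participants who never took a dose, an exclusion that can differ by arm in this open-label trial, and no planned efficacy analysis uses everyone randomized

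*Protocol*

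**What the plan says.** **Estimand.** Protocol Section 3 (United States registration) and SAP 1.1 ask about study-eligible participants, whatever happens to their treatment. The treatment condition is "randomized treatment regardless of treatment discontinuation or initiation of rescue therapy". The population attribute reads "targeted study population. See Section 9.2 for details". On intercurrent events: "The 2 intercurrent events, treatment discontinuation for any reason and initiation of rescue therapy, are addressed by the treatment condition of interest attribute". Never starting treatment is not listed.

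**Analysis sets.** Protocol 9.2 defines mITT as "All randomized participants who took at least 1 dose of LY3209590 or insulin glargine"; SAP Section 3 has "All randomized participants who took at least 1 dose of study treatment". EAS1 and EAS2 are both "mITT Population excluding participants discontinuing the study treatment due to inadvertent enrollment". SAP 4.3.2 uses EAS1 participants with a baseline value for the treatment regimen analysis of HbA1c, and SAP 4.4.1.2 uses the same set for the composite of HbA1c below 7% without nocturnal hypoglycemia.

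**Sensitivity analyses.** SAP 4.3.3.2: "The primary efficacy analysis will be repeated for the mITT population, including participants inadvertently enrolled". SAP 4.4.1.3 does the same for the key secondary endpoints. The Randomized Population is used for disposition and listings (SAP 4.2) and for demographics, baseline characteristics and medical history (SAP 6.1).

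**First dose.** The trial is open-label (protocol 6.3). In the Visit 3 flow (protocol 4.1), assignment comes first, then baseline procedures, training and dosing. LY3209590 is given during the visit (protocol 1.3 and 6.5.1.1). For the comparator: "Insulin glargine can be taken at the site or after the visit depending upon whether the study visit timing coincides" with the participant's usual dosing time. Protocol 6.5.2.1 asks for on-site dosing when the times overlap and does not require it otherwise.

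**The concern.** Taking a first dose is a post-randomization event, and here it happens after the allocation is known. Making it a condition of entry to the primary analysis set removes participants for something they did after learning their arm. Eligibility in protocol 5.1 and 5.2 contains no dosing requirement, so a never-starter is study-eligible in the sense of the clinical question but absent from the analysis that answers it.

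The opportunity to leave undosed is not the same in the two arms. On LY3209590 the gap between assignment and first dose lies within one site visit. On glargine it can extend beyond the visit for participants whose usual dosing time falls elsewhere. Comparable early departures could therefore stay in one arm, as imputed HbA1c values and composite failures, and disappear from the other. If a never-starter did attend Week 26, an observed HbA1c would also be discarded.

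At stake is the comparability that randomization provides in the US primary analysis and in the composite key secondary. As planned, no efficacy result would show whether the exclusion mattered.

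**Working it through.** **1. The plan's own figures.** Inputs from protocol 9.5 and SAP Section 5: 670 randomized 1:1 (335 per arm), 15% dropout, 284 completers per arm, SD 1.1, true difference 0, two-sided 95% CI.
- Completers: 335 × 0.85 = 284.75 per arm, so dropout is already counted from randomization.
- SE = 1.1 × √(2/284) = 0.0923.
- Power = Φ(margin/SE − 1.96): 99.1% at 0.4 and 90.1% at 0.3. The stated values (above 99% and at least 90%) reproduce.

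**2. Assumptions.** Neither document gives a never-dosed rate or outcome. I take k = 3, 7 or 10 of 335 glargine participants excluded, none on LY3209590, and a Week 26 HbA1c that differs from glargine starters by d = 0.5 or 1.0 points, in either direction.

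**3. HbA1c.** Shift in the glargine mean = (k/335) × d.

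| k | k/335 | d = 0.5 | d = 1.0 |
|---|---|---|---|
| 3 | 0.9% | 0.0045 | 0.0090 |
| 7 | 2.1% | 0.0104 | 0.0209 |
| 10 | 3.0% | 0.0149 | 0.0299 |

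The largest shift is about one third of the planned SE (0.0299/0.0923 = 0.32) and 7.5% of the 0.4 margin that SAP 2.1 pairs with this estimand (0.0299/0.4). Against the alternative 0.3 margin in SAP 4.3.2 it is 10%.

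**4. Direction.** The contrast is LY3209590 minus glargine.
- If glargine never-starters would have had higher HbA1c, removing them lowers the glargine mean and works against noninferiority. With k = 7 and d = 1.0, SE = 1.1 × √(1/284 + 1/277) = 0.0929. Power is Φ((0.4 − 0.0209)/0.0929 − 1.96) = 98.3%, and 85.2% at 0.3.
- If they would have had lower HbA1c, removal favours noninferiority. At a true difference equal to the margin, one-sided error is Φ(0.0209/0.0929 − 1.96) = 4.1% instead of 2.5%. For k = 3 and d = 0.5 it is 2.8%. For k = 10 and d = 1.0 it is Φ(0.0299/0.0931 − 1.96) = 5.1%.

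These calculations treat all k as lost completers, which slightly overstates the loss of precision.

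**5. Composite.** Apply the planned 28.7% and 42% to completers and score the 15% dropouts as failures. Glargine: 0.85 × 0.287 = 24.4%. LY3209590: 0.85 × 0.42 = 35.7%. If k of the glargine failures are never-starters and are excluded, the glargine rate is 0.24395 × 335/(335 − k):
- k = 3: 24.6%
- k = 7: 24.9%
- k = 10: 25.1%

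Under this scoring, exclusion from glargine can only raise its rate, which narrows the contrast and works against LY3209590.

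**The case against.** **No direct contradiction.** A reader might set the treatment-condition line against the dose requirement and call them contradictory. They are not: that line concerns discontinuation and rescue, and the population attribute openly defers to the analysis-set section, where the dose requirement stands. This objection holds. What remains is a population conditioned on a post-randomization event that the estimand does not name.

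**Not glargine alone.** A reader might infer that only glargine participants can be lost. The Visit 3 flow does not support this. LY3209590 participants also learn their assignment before baseline procedures, training and dosing, so they too can leave undosed. Some glargine participants are dosed on site: protocol 6.5.2.1 asks for it when times overlap, and protocol 4.1 has morning basal users hold their dose for Visit 3. The documents support unequal opportunity only.

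**Not a recording artefact.** A reader might also infer that someone who takes glargine but has no e-diary entry falls out, because protocol 6.4 sets basal dose recording at one day per week. mITT turns on taking a dose, and the recording frequency is not a membership rule.

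**Partly visible already.** Disposition with reasons is reported by arm on the Randomized Population, and baseline tables are repeated on it if it differs from mITT. A marked imbalance would be seen. Its effect on the endpoints would not.

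**Existing rules do not simply carry over.** The HbA1c baseline is tied to the first-dose day (SAP 4.1), retrieved dropouts are people who discontinued treatment (SAP 4.3.2), and the composite failure rule covers those who discontinued the treatment period (SAP 4.4.1.2). None clearly covers someone never dosed. This stands, and the fix has to supply the rules.

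**Conclusion.** The point holds in limited form. EAS1 excludes randomized participants who never took a dose, never starting is not named as an intercurrent event, the exclusion can differ by arm with more opportunity on glargine, and no planned efficacy or sensitivity analysis includes everyone randomized.

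The likely size is small: about 0.005 to 0.03 HbA1c points and at most about 0.7 percentage points on the glargine composite rate (24.4% to 25.1%). Both depend on assumed counts of 3 to 10, none lost on LY3209590, and, for HbA1c, an assumed difference of 0.5 to 1.0 points. A reader might infer a bias in favour of LY3209590. The documents do not fix the direction for HbA1c, and if never-starters would have done worse, both endpoints move against LY3209590. This is a cheap improvement to the plan and gives no reason to expect a changed conclusion.

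**What to change.** Extend SAP 4.3.3.2 and 4.4.1.3 so that the treatment regimen analyses of HbA1c change and of the composite are repeated on the Randomized Population, stating whether inadvertent enrollees remain excluded or are added separately. The alternative is to define EAS1 on the Randomized Population in protocol 9.2 and SAP Section 3. Either way, state for never-dosed participants:

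- **Baseline:** the last HbA1c on or before Visit 3, with the baseline hypoglycemia period also closing at Visit 3.
- **Week 26:** use any observed HbA1c. Impute missing values by the same retrieved-dropout method, or by return-to-baseline where that method falls back to it, and say whether never-dosed participants with an observed value count as retrieved dropouts.
- **Composite:** score as non-responders.
- **Reporting:** number undosed by arm, with reasons.

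The safety set can stay on dosed participants. The cost is wording, one more analysis and a few more imputed values. No new data are needed, and planned power is unaffected because 670 and the 15% dropout already count from randomization.
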